Repurposing of Fibrinogen Concentrate as a Cost-Effective and Safe Hemostatic Agent in Infants Undergoing Cardiac Surgery on Cardiopulmonary Bypass

Statistical Analysis Plan

NCT03014700

March 8, 2019

[name], Principal Investigator Emory University

[name], Principal Investigator Stanford University

Intention-to-Treat (ITT) Analysis Set

The ITT Analysis Set consists of all enrolled subjects. Efficacy summarization and analysis will be conducted using the ITT analysis set.

Per Protocol Analysis Set (PPAS):

The subset of subjects in the full analysis (ITT) set who complied with the protocol sufficiently (see below) without any major protocol deviations. Confirmatory analysis was performed using the PPAS dataset. Final definition of PPAS were defined prior to data lock. Elements of PPAS may include exclusion criteria such as:

- Violation of inclusion or exclusion criteria
- Did not receive study medication
- Did not go on cardiac bypass during surgical intervention
- Patients unable to wean from bypass in operating room

Statistical Analysis for Primary outcome (using ITT):

The primary analysis followed the ITT principle and was performed using a linear regression adjusted for the randomization strata of institution and complexity of surgery. PP analysis was also performed for the primary outcome of total units of intraoperative allogenic blood transfusions.

Results for Primary outcome:

Patients in the FC group received significantly fewer total units of allogenic blood transfusions when compared to patients in the cryoprecipitate group (5 units [IQR 4.00,7.00] in the ITT analysis and 6 units [IQR 5.00,7.00] in the PP analysis in the control group, and 4 units [IQR 3.00,5.00] in the ITT analysis and 4 units [IQR 3.00,5.00] in the PP analysis in the study group). In the ITT analysis, the FC group received a mean of 1.61 [95% CI 0.3-2.91, p-value =0.02] less allogenic donor exposures than the cryoprecipitate group when adjusted for institution and complexity. In a PP analysis, the FC group received a mean of 2.67 [95% CI 1.75-3.59, p-value <0.001] less allogenic donor exposures than the cryoprecipitate group when adjusted for institution and complexity.

Statistical Analysis for Secondary Outcomes (using Per Protocol population)

In secondary analyses, we used a Mann-Whitney U test to test whether the secondary outcomes measured continuously differed by arm. For categorical secondary outcomes, we used a Chi-squared test when the expected count in each cell was > 5, otherwise we used a Fisher's exact test. All secondary analyses were conducted on the subset of PP patients. Sensitivity analyses were performed for the secondary outcomes adjusting for site, complexity, weight, and CPB time. For continuous outcomes, we log-transformed the secondary outcomes then fit a linear regression model and for the outcome of any AE, we fit a logistic regression model.

Sample Size Justification: We designed our study to have 90% power to detect a reduction of two allogenic blood product transfusions when assuming that the mean number of units in patients receiving cryoprecipitate was 7 with a standard deviation of 2.2 units in both arms. Using a two-sample t-test and performing a two-sided test with an alpha = 0.05 we found that 27 patients per arm were needed. We assumed approximately 10% of patients would be missing their primary outcome and enrolled 30 patients per arm.

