## Study Description:

This study is a prospective, randomized trial designed to evaluate the role of fibrinogen concentrate versus cryoprecipitate in reducing allogenic donor exposures in infants undergoing cardiac surgery with CPB. Prior to surgery, we will randomize infants undergoing cardiac surgery to receive cryoprecipitate (standard of care) or fibrinogen concentrate (study arm) as part of a post-bypass transfusion algorithm. For patients enrolled in the study, we will follow our standard anesthetic management, cardiopulmonary bypass protocol, and transfusion thresholds in the operating room and ICU.

In each patient, results from our standard of care labs will be obtained at seven different time points:

- 1) Preoperative labs (for outpatients, preoperative baseline labs are obtained in the preoperative clinic; for inpatients, baseline labs are obtained in the hospital the day before surgery) (CBC, Coagulation tests, Fibrinogen, Chemistry),
- 2) After induction of anesthesia but prior to surgical incision (ABG, TEG),
- 3) 10min after initiation of CPB (TEG, Fibrinogen, ABG),
- 4) After termination of CPB, protamine reversal and first cryoprecipitate/FC administration (ABG, TEG, fibrinogen),
- 5) After chest closure or placement of silastic patch if chest remains open (ABG, TEG),
- 6) Coagulation labs on immediate arrival to the ICU as per ICU protocol (ABG, Fibrinogen, Coagulation studies, CBC, Chemistry), and
- 7) On the morning of the first post-operative day in the ICU as per ICU protocol (fibrinogen, ABG, coagulation studies, chemistry, CBC).

Blood samples drawn prior to surgery (i.e time number 1) will be done either by our clinical laboratory for outpatients or by hospital protocol for inpatients. For all other time points, blood samples will be drawn from an indwelling line placed for the surgery.

After separation from bypass, patients will receive either cryoprecipitate or FC, depending on their randomization group. For patients randomized to the study arm, the fibrinogen level measured on bypass will be used to calculate the appropriate dose of fibrinogen concentrate to achieve a level of 300mg/dL after separation from bypass. In these patients, FC will replace cryoprecipitate in our post-bypass transfusion algorithm

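### Does calling the per-protocol analysis of transfused units confirmatory require a change to the SAP?

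*SAP*

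**What the plan says.** The SAP defines the ITT set as everyone enrolled and assigns efficacy analysis to it. Its primary-outcome section repeats ITT in the heading and specifies a linear regression with institution and surgical complexity as covariates. It then adds that a per-protocol (PP) analysis of the same outcome was also done.

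The paragraph on the Per Protocol Analysis Set (PPAS) contains the sentence at issue: "Confirmatory analysis was performed using the PPAS dataset". The next sentence says that the final definition was settled before data lock. A list of examples follows, introduced by "Elements of PPAS may include exclusion criteria such as". It names eligibility violations and three further elements: "Did not receive study medication", "Did not go on cardiac bypass during surgical intervention" and "Patients unable to wean from bypass in operating room".

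On results, the SAP gives the control medians as "5 units [IQR 4.00,7.00] in the ITT analysis and 6 units [IQR 5.00,7.00] in the PP analysis in the control group". The FC median is 4 in both sets. The adjusted ITT difference is 1.61 (95% CI 0.3 to 2.91, p=0.02). For PP: "In a PP analysis, the FC group received a mean of 2.67 [95% CI 1.75-3.59, p-value <0.001] less allogenic donor exposures".

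Two parts of the protocol matter. Its Study Description randomises before surgery and says "After separation from bypass, patients will receive either cryoprecipitate or FC, depending on their randomization group". Its Sample Size section counts each unit of red cells, plasma, cryoprecipitate and platelets as one donor exposure. FC is not among the counted products.

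**The concern.** In trial statistics, confirmatory usually denotes the analysis that carries the claim. Two analyses of one outcome cannot both hold that status without an order or a split of alpha, and the SAP gives neither.

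PP is also the weaker candidate. Three of its four example exclusions happen after randomisation, so the comparison is no longer protected by it. The non-receipt rule raises a more specific worry. A control who received no cryoprecipitate has no counted units from the assigned product, and removing that patient raises the control mean. The same rule in the FC arm acts on a product that is not counted. If the rule covers controls, it selects on part of the outcome in one arm only.

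The reported figures move in that direction: the control median rises, the FC median does not, and the difference grows by two thirds. A reader who took 2.67 (p<0.001) as confirmed could overstate the benefit.

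**Working it through.** **1. Reproduce the reported ITT result.** Assume 60 patients and 56 residual degrees of freedom (t = 2.003).
- Half-width: (2.91 − 0.3)/2 = 1.305.
- SE: 1.305/2.003 = 0.651.
- t: 1.61/0.651 = 2.47, so p = 0.017. The SAP's 0.02 reproduces.

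**2. Compare with PP.** The size of the PP set is not given.
- Half-width: (3.59 − 1.75)/2 = 0.92; ratio to ITT 0.92/1.305 = 0.705.
- SE: 0.454 to 0.459 across assumed sizes of 40 to 60.
- Shift: 2.67 − 1.61 = 1.06, or 66% of 1.61.

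**3. Were the exclusions random?** If n of 60 are kept at random, the shift has SD of about 0.651 × √(60/n − 1). This is 0.22 at n = 54 and 0.46 at n = 40, so 1.06 is 4.9 to 2.3 SDs. The residual SD under ITT is 0.651 × √15 = 2.52. At that SD the PP precision would need about 4 × (2.52/0.465)² ≈ 118 patients, against 60 enrolled. The exclusions were therefore related to transfusion. This does not identify the rule responsible.

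**4. How much shift needs no bias?** The protocol expects FC to replace two units of cryoprecipitate. If a fraction q of controls received none, and FC changes nothing else, ITT estimates 2(1 − q) and an unbiased PP analysis estimates 2. The gap is 2q: 0.2, 0.4 or 0.6 at q = 10%, 20% or 30% (assumed values). Against 2.00, the PP estimate gives (2.67 − 2.00)/0.458 = 1.46, p about 0.15. So 2.67 is compatible with plain substitution and no bias, although this does not prove that bias is absent.

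**5. Does the non-receipt rule explain the pattern?** An illustrative simulation used 30 per arm, two cryoprecipitate units for each control unless skipped, and no FC effect on other products. It is not a fit to the data.

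| Assumption about skipping the first product | Added bias (units) |
|---|---|
| Unrelated to bleeding, or equal in both arms | 0 |
| 20–30% of controls, 10% of FC, correlation 0.5–0.8 | 0.13 to 0.50 |
| Controls only, correlation 0.5–0.8 | 0.17 to 0.79 |

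Alone, the rule gave a mean CI-width ratio of 0.84 to 1.08 and reached 0.705 in at most 2.3% of runs. Removing two patients with 15 units each gave a ratio of 0.70 with no bias, but never a shift of 1.06. No single mechanism reproduces the reported figures well.

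**6. What would relabelling change?** The sample size rests on a two-unit difference, SD 2.2, two-sided 0.05 and 90% power. The t-based calculation gives 26.4, so 27 per arm, and 27/0.9 = 30; both stand. If either test could support the claim at 0.05, the type I error would be at most 0.10 (0.0975 if independent, lower with this overlap). ITT is designated primary and meets 0.05 itself, so the claim does not use that route.

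**The case for a change.** The strongest case for a change is that the correction costs one word, the ambiguity is real, and the shift is large and goes the way selection on cryoprecipitate would push it. Fixing the PPAS before data lock limits data-driven choice of the set, but it does not restore the balance lost by conditioning on later events. Removing heavily transfused patients cannot raise the control median from 5 to 6 or its lower quartile from 4 to 5, so some controls with few units must have left the set. A re-run that keeps patients who received no product, with exclusions tabulated by arm and reason, might show where the rise came from.

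Part of this stands. PP is properly read as supportive, and the exclusions were not random. The rest does not lead to a change:
- Controls with few units could have left because they never went on bypass, with no selection on receipt of product.
- The bias needs four things that the documents do not show: that the non-receipt rule was in the final PPAS, that study medication includes cryoprecipitate, that controls skipped product more often than FC patients, and that skipping tracked low bleeding. The Study Description puts no bleeding condition on the first product.
- The re-run would not settle the question. With 20% of controls skipping and two extreme patients excluded, it averaged 1.61, 1.60 and 1.60 at correlations 0, 0.5 and 0.8, while PP averaged 2.01, 2.30 and 2.49. It falls back to about 1.6 with or without bias, and dividing the drop between undiluted effect and bias requires the true effect in treated patients. The exclusions also overlap, since a patient who never goes on bypass would ordinarily receive neither product.

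**Conclusion.** No change to the plan is needed. The wording is loose, but the SAP's structure is clear: ITT is the efficacy set and the primary analysis, and PP was run in addition. In that setting the sentence is best read as saying that PP was used to confirm the ITT finding. The conclusion rests on 1.61 units (95% CI 0.3 to 2.91, p=0.02), and no choice of label alters it.

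The 1.06-unit rise to 2.67 should be reported as supportive. Anyone writing up the trial would sensibly say what counted as study medication and list exclusions by arm and reason. That is reporting detail and does not correct the analysis. Bias in PP is possible but not shown: under the assumed skip rates it ranges from 0 to 0.79 units, and the documents do not narrow that range.

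This rests on reading the ITT statements as governing the primary outcome, and on 60 patients in the ITT model. If a publication presented 2.67 as the trial's main estimate, the objection would apply to that publication. The SAP's use of the PP set for secondary outcomes is a separate matter and is not judged here.

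### The lead secondary tests leave out the randomisation strata that the primary analysis uses, and no described analysis uses the preoperative labs; precision is lost if the strata or the labs are prognostic

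*SAP*

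**What the plan says.** - **Primary outcome.** Under its primary-outcome heading, the SAP describes an ITT analysis "performed using a linear regression adjusted for the randomization strata of institution and complexity of surgery".
- **Continuous secondary outcomes.** Under its secondary-outcomes heading: "we used a Mann-Whitney U test to test whether the secondary outcomes measured continuously differed by arm". No stratum or covariate enters.
- **Categorical secondary outcomes.** "we used a Chi-squared test when the expected count in each cell was > 5, otherwise we used a Fisher's exact test". Again there are no strata.
- **Analysis set.** All secondary analyses use the per-protocol subset.
- **Sensitivity analyses.** "Sensitivity analyses were performed for the secondary outcomes adjusting for site, complexity, weight, and CPB time". Their form is: "we log-transformed the secondary outcomes then fit a linear regression model and for the outcome of any AE, we fit a logistic regression model".
- **Baseline labs.** The protocol's Study Description has preoperative labs for outpatients and inpatients; for inpatients, "baseline labs are obtained in the hospital the day before surgery) (CBC, Coagulation tests, Fibrinogen, Chemistry". Specific Aim #2 makes coagulation labs an outcome, and its methods text adds hematocrit, fibrinogen and thrombelastogram values. No described analysis, main or sensitivity, uses a preoperative laboratory value.

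**The concern.** The SAP follows the randomisation design in its primary analysis and gives no reason for dropping it in the lead secondary tests. Ventilation time, stay and adverse events could plausibly vary with site practice and surgical complexity. When arms are balanced within strata, stratum differences cannot contribute to the difference between arms. An unstratified test still counts them as noise, so its standard error is too large for the design.

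The sensitivity analyses close only part of the gap:

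- They add weight and CPB time to the strata and move continuous outcomes to the log scale. A disagreement with the Mann-Whitney result could come from scale, covariates or strata.
- The only categorical model described is for any AE. Nothing strata-adjusted is described for other categorical outcomes, such as the infection and thrombosis risks named in Specific Aim #2.

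Aim 2 asks about safety and effectiveness in 60 infants, fewer once per-protocol exclusions are made. A missed difference is a real risk at that size, so precision that existing data could supply should not be given up.

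**Working it through.** **1. The plan's own figure.** The SAP sizes only the primary outcome: difference 2, SD 2.2, two-sided alpha 0.05, power 90%. The normal formula gives 2 × (1.96 + 1.2816)² × 2.2² / 2² = 25.4, so 26 per arm. The t-test version gives 26.4, so 27, and 27 / 0.9 = 30. The stated 27 and 30 reproduce. No secondary outcome has a stated power.

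**2. Size by formula.** Let R² be the share of outcome variance explained by the strata, with allocation balanced within them. The true standard error is √(1 − R²) times the one the unstratified test uses, so its type I error is 2 × P(Z > 1.96 / √(1 − R²)):

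- R² 10%: 1.96 / 0.949 = 2.066, type I error 0.039
- R² 25%: 1.96 / 0.866 = 2.263, type I error 0.024
- R² 50%: 1.96 / 0.707 = 2.772, type I error 0.006

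**3. Simulation.** The assumptions, none of them given in the documents, are: 60 patients, 2 sites × 2 complexity levels, permuted blocks of 4 within stratum, normal outcomes and a standardised effect of 0.7. There were 4,000 null runs (Monte Carlo SE about √(0.05 × 0.95 / 4000) = 0.003) and 2,000 power runs (about √(0.75 × 0.25 / 2000) = 0.010).

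| Strata R² | Mann-Whitney type I | Power: Mann-Whitney | Power: unadjusted t-test | Power: van Elteren | Power: regression on strata |
|---|---|---|---|---|---|
| 0% | 0.050 | 0.74 | 0.76 | 0.71 | 0.77 |
| 10% | 0.038 | 0.75 | 0.78 | 0.77 | 0.81 |
| 25% | 0.026 | 0.76 | 0.80 | 0.84 | 0.88 |
| 50% | 0.006 | 0.77 | 0.83 | 0.95 | 0.96 |

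The strata-adjusted tests held type I error at 0.043 to 0.054. Against regression on the strata, Mann-Whitney loses about 6 points at 10% (0.811 − 0.750) and 12 at 25% (0.884 − 0.763). About 3 points of each gap (0.765 − 0.737 at 0%) reflect rank test versus t-test on normal data rather than the strata. Like for like, van Elteren gains about 2 and 7 points over Mann-Whitney.

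**4. Baseline lab.** With strata R² 0% and a baseline value explaining 25% of variance (assumed), Mann-Whitney type I error is 0.046, so omission does not make the test conservative. Adding the value raises regression power from 0.77 to 0.87. In general the standard error falls by 1 − √(1 − r²): about 5% at r = 0.3 and 20% at r = 0.6, both values assumed.

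**5. Per-protocol subset.** Its size is not given. With 15% of patients removed at random, Mann-Whitney type I error is 0.042, 0.034, 0.025 and 0.011 at strata R² of 0%, 10%, 25% and 50%. Random removal is the favourable case; real exclusions need not be random.

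**6. Do the documents show prognostic strata?** The adjusted ITT interval (0.3 to 2.91) gives SE = 1.305 / 2.003 = 0.651. At 30 per arm the residual SD is 0.651 / √(2/30) = 2.5, no smaller than the planned 2.2. The per-protocol interval (1.75 to 3.59) gives SE = 0.92 / 2.003 = 0.459 and SD 1.8 at 30 per arm, less if fewer were analysed. Both concern the primary outcome, and the exclusions may themselves explain the second. Neither settles R² for a secondary outcome.

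**The case against.** **The strata are already handled.** A reader might infer that the secondary analyses ignore the strata altogether. They do not: the sensitivity models adjust for site and complexity. What remains is which analysis leads, what is bundled with the strata, the categorical outcomes other than any AE, and the missing baseline labs.

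**Conservatism is conditional.** It is tempting to say that the secondary p-values are simply too conservative. That needs balance within strata and prognostic strata. The SAP names the strata but describes no blocking, and the protocol's randomisation text does not mention stratification. At R² 0% the Mann-Whitney test has its nominal size.

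**The per-protocol subset can push either way.** Possible exclusions include not receiving study medication and failure to wean from bypass, both arising after randomisation. The primary estimate moves from 1.61 (ITT) to 2.67 (per protocol), so selection matters here. Nobody should read the reported p-values as erring on the safe side.

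**Baseline labs are a separate matter.** A reader might add them as a cause of conservatism; step 4 shows they are not. The gain is also uncertain for fibrinogen: FC dosing aims at a fixed target from the on-bypass level, which may weaken the link with the preoperative value in that arm.

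**Unadjusted tests were the protocol's plan, and the repair has a price.** The protocol specifies analysis of variance, chi-squared and Fisher tests. Van Elteren gives up a little power if the strata are not prognostic (0.71 against 0.74).

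All of this stands and limits the claim. None of it gives a reason to lead with analyses that leave out the strata.

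**Conclusion.** The point holds in conditional form. The lead secondary tests omit strata that the SAP itself uses for the primary outcome, and no described analysis uses the preoperative labs. At strata R² of 10% to 25%, the unstratified Mann-Whitney test would run at a type I error of about 0.04 to 0.026 and give up about 6 to 12 points of power against regression on the strata. At 0% there is no conservatism and little to gain. These sizes rest on balanced allocation within strata, normal outcomes, an effect of 0.7 SD and assumed R² values. Leaving out a preoperative lab affects precision only. The net direction of error in the reported per-protocol p-values is unknown.

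Severity is modest. Only secondary outcomes are involved, adjusted models exist for continuous outcomes and any AE, and this feature creates no extra false positives.

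**What to change.** - **Continuous secondary outcomes:** lead with regression on arm, institution and complexity, stating the scale for each outcome, or with van Elteren where a rank test is preferred.
- **Categorical secondary outcomes, all of them:** lead with a Cochran-Mantel-Haenszel test by institution and complexity, exact or with pooled strata where counts are sparse.
- **Post-operative laboratory outcomes with a preoperative value** (fibrinogen, hematocrit from the CBC, coagulation tests): use regression on arm and strata with that value as a covariate. The thrombelastogram is not among the preoperative labs at the first time point.
- **Unstratified tests:** keep them as supportive and report them beside the lead result for every outcome, so that the choice of test is not selective.
- **Labelling:** call the change post hoc, since the SAP already reports primary results.

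The cost is SAP wording and a rerun on data already held. The downsides are a slight loss with van Elteren if the strata are not prognostic, and possible pooling of small strata. Adjusting for strata does not remove selection into the per-protocol subset, so that caveat should stay with the results.

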### Specific Aim #2:

Comparison of fibrinogen concentrate to cryoprecipitate as a safe and effective hemostatic agent:

By evaluating the laboratory values, transfusion requirements, and outcomes, we will examine the effectiveness of FC in reducing transfusion related risks, such as 1) length of mechanical ventilation time, 2) length of ICU stay, 3) length of hospital stay, 4) adverse events within seven days of surgery, 5) preoperative and post-operative coagulation laboratory values.

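### All secondary outcomes, adverse events included, are compared only in the per-protocol set despite the SAP's own ITT rule, and no safety set is defined

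*SAP*

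**What the plan says.** The SAP defines two analysis sets. Under the ITT heading, which covers all enrolled subjects, it states: "Efficacy summarization and analysis will be conducted using the ITT analysis set". The PP set is the part of ITT without major protocol deviations. On its role the SAP says: "Confirmatory analysis was performed using the PPAS dataset. Final definition of PPAS were defined prior to data lock". The exclusions are introduced by "Elements of PPAS may include exclusion criteria such as". Four examples follow: breach of the entry criteria, no study product received, no bypass during the operation, and failure to come off bypass in theatre.

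The primary outcome is analysed in ITT, with PP in addition. For secondary outcomes the section heading names the PP population and the text repeats it: "All secondary analyses were conducted on the subset of PP patients". The SAP continues: "Sensitivity analyses were performed for the secondary outcomes adjusting for site, complexity, weight, and CPB time". Adverse events belong to the same section: "for the outcome of any AE, we fit a logistic regression model".

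The Protocol's Specific Aim #2 compares the two products for safety as well as effect. It lists "adverse events within seven days of surgery" together with ventilation time, the two lengths of stay and coagulation results. The Study Description places randomisation before surgery and gives the allocated product after separation from bypass.

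**The concern.** The general rule and the secondary-outcome rule point to different populations, and no reason is given for the change. The sensitivity analyses vary the covariates and leave the population alone. PP is called confirmatory, but no ITT analysis of any secondary outcome is described for it to confirm.

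The consequence is loss of the randomised comparison. Apart from transfusion units, which are analysed in ITT, every outcome serving Aim 2 is compared only among patients who may have been selected after allocation. If the selection differs between arms, or removes patients with unusual courses, the arms compared are no longer the arms randomised. The reader has no ITT result to check against.

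For adverse events the position is weaker still. The documents do not say whether these fall under the ITT efficacy rule, and there is no safety set to catch them if they do not. The case-by-case and quarterly reviews in the Protocol's Adverse Events Reporting and Data Safety Monitoring Plan are monitoring. They do not compare the arms.

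**Working it through.** **1. Populations side by side (SAP; timing from the Protocol)**

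| Item | Set described |
|---|---|
| Efficacy, general rule | ITT |
| Primary outcome | ITT, plus PP |
| Continuous and categorical secondary outcomes | PP only |
| Covariate-adjusted sensitivity analyses | PP (no other set named) |
| Any adverse event | PP only |
| Safety set | none defined |

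Because randomisation precedes surgery, no product, no bypass and no weaning all occur after it. Entry-criteria violations normally reflect baseline status.

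**2. The SAP's reported primary results**

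Standard error = half-width of the CI / t(0.975). I assume 56 degrees of freedom for ITT (60 patients less 4 model terms) and 40 to 56 for PP, whose size is not given.

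- ITT: half-width (2.91 − 0.30)/2 = 1.305; SE ≈ 0.651; t = 1.61/0.651 ≈ 2.47; p ≈ 0.017. The SAP gives 0.02.
- PP: half-width (3.59 − 1.75)/2 = 0.92; SE ≈ 0.455 to 0.459; t ≈ 5.8 to 5.9; p < 0.00001. The SAP gives < 0.001.

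The reported figures are internally consistent.

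**3. Does the choice of set matter where it can be seen?**

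- Shift in the adjusted difference: 2.67 − 1.61 = 1.06 units; 2.67/1.61 = 1.66, so +66%.
- The PP estimate lies inside the ITT interval: 0.30 < 2.67 < 2.91.
- CI width falls from 2.61 (ITT) to 1.84 (PP), although PP cannot contain more patients.
- The control summary moves from 5 [4, 7] in ITT to 6 [5, 7] in PP. PP is a subset of ITT, so at least one control patient was removed. The FC summary is 4 [3, 5] in both.

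This gap does not transfer directly to other outcomes. Under the Protocol's Sample Size/Statistical Analysis, cryoprecipitate units count as donor exposures. Dropping controls who received no cryoprecipitate would therefore raise the control mean mechanically. That route does not apply to ventilation, stay or laboratory values.

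**4. How far could exclusions move an adverse event rate?**

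Inputs: n = 30 in the arm (SAP, Sample Size Justification: 27/(1 − 0.10) = 30). The number of patients with an event, E, and the number excluded, k, are my assumptions. Exclusions are taken in one arm only.

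- Lowest PP rate = max(E − k, 0)/(n − k)
- Highest PP rate = min(E, n − k)/(n − k)

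| True rate | k | Lowest | Highest |
|---|---|---|---|
| 6/30 = 20% | 1 | 5/29 = 17.2% | 6/29 = 20.7% |
| 6/30 = 20% | 3 | 3/27 = 11.1% | 6/27 = 22.2% |
| 6/30 = 20% | 6 | 0/24 = 0% | 6/24 = 25.0% |
| 3/30 = 10% | 3 | 0/27 = 0% | 3/27 = 11.1% |
| 12/30 = 40% | 3 | 9/27 = 33.3% | 12/27 = 44.4% |

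These are extremes, shown for scale. The error can go in either direction.

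**The case against.** The strongest reply is that a specific rule overrides a general one. The PP choice for secondary outcomes is stated twice, the ITT sentence can be read as meaning the primary outcome, and nobody is misled about which set was used. That reading is possible, but the ITT sentence does not limit itself to the primary outcome, and Aim 2 treats ventilation, stay and laboratory values as measures of effectiveness. Even if it is accepted, the departure from ITT is unexplained and the randomised comparison is still absent.

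The second reply concerns timing. Product is due after separation from bypass, so absence of bypass and failure to wean come before it and cannot be caused by it. Among the listed criteria, non-receipt of product is the one most likely to depend on arm. A safety set of infants who received product would also largely overlap PP. This stands, and it limits how much bias to expect. It does not cover treated infants excluded for eligibility or other major deviations, whose number is unknown and may be zero.

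Third, some post-bypass laboratory values do not exist for patients without bypass or product, and a PP analysis is informative for the Protocol's question of whether FC performs no worse than cryoprecipitate. Both points are fair. They support showing PP beside ITT, not PP alone.

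Finally, the PP definition was fixed before data lock. That guards against choosing exclusions after seeing the locked data. It does not restore the randomised groups, and the definition printed in the SAP remains an open list.

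**Conclusion.** The concern holds and should be fixed. The mismatch between the ITT rule and the PP-only secondary analyses, and the absence of a safety set, can be read directly from the SAP; confidence in that is high. The size and direction of any bias in the secondary outcomes are unknown, because neither exclusions by arm nor secondary results are given. The primary outcome shows that the two sets differ materially (a shift of 1.06 units), but it is not a measure of bias elsewhere. The adverse event ranges rest on assumed event and exclusion counts.

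**What to change.** - Repeat the Mann-Whitney, chi-squared or Fisher tests and the adjusted models for the secondary outcomes in the ITT set, and report PP beside them. For post-bypass laboratory values, state how many patients have no value and why. State also how the adjusted models handle CPB time for any patient who did not go on bypass.
- Compare adverse events within seven days in a defined safety set not limited to PP. Say explicitly whether it is all randomised patients or all who received product. Because the second option overlaps PP heavily, the all-randomised comparison should be available as well.
- Print the final PP definition and a table of exclusions by arm and reason.
- Reconcile the ITT sentence with the secondary-outcome section. Because the SAP already reports results, label the added analyses as not prespecified.

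The cost is a rerun of existing tests on data the Protocol says are recorded, one table and a wording change. The drawbacks are some missing post-bypass laboratory values, possibly less precise secondary comparisons, and the post hoc status of the additions.
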